6.4.6 Target volumes and safety margins (CTV and PTV)

CTV definition in both arms of the trial should follow the ESTRO guidelines for early breast cancer [49]; however, in case of locally advanced disease (e.g. T4 or N2/3 disease), CTVs need to be adjusted to ensure that all macroscopic tumor tissue is encompassed with at least a 5 mm safety margin.

Experimental arm (preoperative radiotherapy)

CTVb_low = total breast (excluding 5 mm below the skin) including the initial tumor volume + 5mm [+ 2cm skin in case of inflammatory cancer]
(Anatomically adjusted)

GTVp = primary tumor at the time of radiotherapy.

For CR = boost or no boost (GTVp) is indicated (as decided by the local institution)

Based on the presently available evidence, the clinical significance of administering a boost in the neoadjuvant radiotherapy setting subsequent to achieving complete remission via neoadjuvant chemotherapy remains uncertain. Consequently, a universal recommendation cannot be made, as it is contingent upon the cumulative experiences and expertise of the treating institution. In the context of this study, the participating study site will establish, at the outset, whether a boost will be implemented in this particular scenario. Following this determination, all patients within the given study site will receive treatment in accordance with the predetermined local decision.

In cases where clinical complete remission is achieved during the initial therapy and no boost is applied but histological evidence of tumor cells is subsequently detected following complete resection, the decision regarding boost administration after surgery becomes uncertain. The value of a boost in this specific situation, along with the radiobiological concerns associated with a prolonged treatment interruption, raises doubts about its role. Therefore, based on the available scientific evidence, it is not recommended to include boost administration in the protocol for these cases.

GTVn = marked + enlarged LK at time of radiotherapy

CTVp_high = GTVp + 0.5cm

(Anatomically adjusted)

CTVn = GTVn + 5mm + Level 1-2 (upper border 1 cm below V. axillares) + Level 3-4 + IMC (if indicated according to protocol)

PTVb_low = **CTVb_low** + 5-8 mm

PTVb_high = **CTVp_high** + 5-8 mm

PTVn = **CTVn** + 5-8 mm

No Gaps between **PTVb_low** and **PTVn** allowed

PTV concept in case of axillary lymph node irradiation

In axillary lymph node irradiation, the PTV should be limited below the level of the axillary vein at a distance of 0.5cm to prevent lymphedema, unless positive lymph nodes including a 0.5cm CTV margin, cross this virtual boundary. Positive lymph nodes should be contoured with a margin of 0.5 cm. If a lymph node including a safety margin extends outside the PTV this volume should be added to the CTV.

Patients with initially negative clinical lymph node (cN0) and neoadjuvant therapy-induced negative pathologic lymph node (ycN0) status on biopsy, but subsequently found to have histologically confirmed lymph node metastases at the time of surgery, who did not receive radiation to the axillary lymph node (ALN) region in the experimental arm are recommended for postoperative radiotherapy of the lymph node regions with field margin connection. It is important to note that cumulative toxicities should be considered in both treatment plans, and the cumulative dose limits of organs should be adhered to without accounting for potential recoveries (as significant recovery within such a short timeframe is unlikely). Efforts should be made to minimize anatomical shifts between the two planning CTs to minimize additional uncertainties. The patient should be adequately informed about the potential for increased cumulative toxicity. In these cases, it is advisable to involve the study leadership closely in the planning and implementation of the therapy.

Standard Arm (postoperative radiotherapy)

In case of breast conserving surgery:

CTVb_low = total breast (excluding 5 mm below the skin) including the initial tumor volume + 5mm [+ 2cm skin in case of inflammatory cancer]
(Anatomically adjusted)

GTVp = tumor bed of the primary tumor (best marked by clips)

CTVp_high = GTVp + 0.5cm (Indication according to AGO guidelines)
(Anatomically adjusted)

CTVn = Level 3-4 + IMC (Indication according to AGO guidelines). Level 1+2 in case of remaining macroscopic tumor and insufficient axillary surgery (see AGO guidelines)

In case of mastectomy:

CTVlow_chestwall (after mastectomy without reconstruction):

CTV definition regarding chest wall postmastectomy radiotherapy (standard arm only) in case of no reconstruction should follow the RTOG recommendations

(<https://www.srobf.cz/downloads/cilove-objemy/breastcanceratlas.pdf>). However, the inclusion of the ribs and the intercostal muscles into the CTV is only recommended in case of tumor infiltration before starting neoadjuvant systemic treatment and should be restricted to the initial area of infiltration +5 mm.

CTVlow_chestwall (after immediate breast reconstruction):

CTV definition regarding chest wall postmastectomy radiotherapy (standard arm only) in case of immediate reconstruction (implant or flap) should follow the ESTRO ACROP consensus guideline (Kaidar-Person et al. 2019, PMID: 31108277):

The implant and the contralateral breast should be delineated using a planning-CT. The transplanted tissues (skin; fat; muscle) and synthetic materials (implant, tissue expander, acellular dermal matrix [ADM]) are not part of the CTV. They should be contoured as organs at risk (OAR), without the aim of compromising the CTVlow_chestwall coverage. Other OARs that should be delineated for treatment planning purposes include heart, lungs, liver, thyroid and, in case of axillary lymph node irradiation with a regional boost, the brachial plexus.

CTVlow_chestwall after immediate breast reconstruction using retro-pectoral implant.

If the dorsal fascia of the breast is not involved by cancer, the CTVlow_chestwall for PMRT does not include the deep lymphatic plexus and therefore only includes the rim of tissue ventral to the major pectoral muscle and the implant, except at the medial, lateral and caudal borders where it may extend to the ventral side of the chest wall where it is not covered by the pre-surgical extension of the major pectoral muscle. Thus, the implant can be largely excluded from the CTVlow_chestwall, whilst the parts of the chest wall surrounding the pectoral muscle around which the lymphatics flow should still be included. As the pectoral muscle overlying the implant is very thin in some women, the muscle would inevitably be included at least partially in the CTV, meaning that the dorsal margin of the CTV would be at the ventral side of the implant.

For patients with adverse factors and/or where the tumor was localised in areas within the breast close to the dorsal fascia (tumor on ink at the dorsal fascia) that was not covered by the major pectoral muscle (mainly caudally located tumors that are often located adjacent to the intercostal muscles and ribs), only separated by the dorsal breast fascia, we recommend to delineate the tissue between the chest wall and the implant caudal from the pre-surgical position of the major pectoral muscle (ideally marked by surgical clips), which can be done as a separate dorsal CTV

CTVlow_chestwall after immediate breast reconstruction with pre-pectoral implant

After IBR-i using a pre-pectoral positioned implant, the CTVlow_chestwall is composed of 2 parts as the pre-pectoral volume is divided into 2 parts by the implant:

1. the ventral part between the skin and the implant, containing the subcutaneous lymphatic plexus and eventual residual glandular tissue
2. the dorsal part between the implant and the pectoral muscle/chest wall, containing eventual residual glandular tissue: only to be included in case of the presence of adverse tumor factors

Indications for including a volume posterior to the implant in the CTVlow_chestwall

Partial inclusion in retro-pectoral implant positioning: in case of the presence of adverse factors and/or if the tumor was localised in areas within the breast close to the dorsal fascia that was not covered by the initial position of the major pectoral muscle: separate volume.

Complete inclusion in pre-pectoral implant positioning: in case of the presence of adverse factors:

- Large primary breast cancer (pT3/pT4, inflammatory cancer)
- Locally advanced breast cancer (LABC) with non-pathological complete response to primary systemic therapy
- Invasion of the major pectoral muscle and/or the chest wall

CTVn (regional lymph nodes)

CTV definition of the regional lymph nodes in case of postmastectomy radiotherapy (with or without immediate reconstruction (standard arm only) should follow the ESTRO guidelines for early breast cancer [49]; however, the CTV for level IV needs to be adjusted to ensure that the region of initially involved lymph in the supraclavicular area is encompassed with at least a 5 mm safety margin. An additional boost radiotherapy after mastectomy is restricted to documented R1 or R2 resections. In the case of R1 resection the CTC_R1/R2 includes the suspect volume + 5 mm. A boost dose of 4x 2.7 Gy in case of R1- and 6x 2.7 Gy in case of R2-resection is recommended.

6.4.7 Radiotherapy Dose Prescription and Specification

The prescribed radiotherapy doses are based on the S3/AGO guidelines for breast cancer. The target volumes will receive following radiotherapy doses:

- PTV (breast): 40,5 Gy in 15 fractions (2,7 Gy daily)
- PTV (RNI): 40.5 Gy in 15 fractions (2.7 Gy daily)
- PTV boost (sequential): 10.5 Gy in 3 fractions (3.5Gy daily).

The radiotherapy dose will be defined ICRU-conform. 3D, IMRT (intensity modulated radiotherapy) and VMAT (volumetric modulated arc therapy) can be used. In left sided breast-cancer respiratory gating (deep inspiration breath hold) is strongly recommended.

Sequential

Boost

PTVb+n_low	15	2.7Gy	40.5Gy
PTVp_high	03	3.5Gy	10.5Gy
PTVn_high			
Total	18		51.0Gy

SIB

PTVb+n_low	15	2.7Gy	40.5Gy
PTVp_high	15	3.2Gy	48Gy
PTVn_high			

IOERT

IOERT	01	10Gy	10Gy
PTVb+n_low	15	2.7Gy	40.5Gy
PTVn_high	15	3.2Gy	
Total	16		50.5Gy

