4.4 Standard of care arm

Patients randomized to the standard of care arm will receive surgery according to the national S3 and AGO-guidelines including targeted axillary dissection (TAD), sentinel lymph node biopsy (SLNB) +/- axilla dissection (AD).

3-6 weeks later, when wound healing is complete, the adjuvant radiotherapy to the whole breast/chestwall will be administered.

According to the S3/AGO guidelines postoperative radiotherapy of the breast/chest wall +/- regional lymph nodes (5x 2.7 Gy per week to 40.5 Gy) is recommended. If indicated according S3/AGO guidelines, a boost radiotherapy (optional intraoperative radiotherapy with electrons = IOERT) should be administered either as simultaneous integrated Boost or as sequential boost (see below).

After breast conserving surgery:

Whole breast radiotherapy with 5x2.7 Gy/week → 40.5 Gy in 3 weeks
+/- boost either as integrated boost (5x 3.2 Gy, total dose 48 Gy) or as sequential boost (3x 3.5 Gy to 10.5 Gy, total dose 51 Gy) or intraoperative boost with IOERT (electrons 1x10 Gy)
+/- + lymph node irradiation (5x2.7 Gy/week → 40.5 Gy in 3 weeks)

After mastectomy:

- chest wall irradiation: 5x2.7 Gy/week → 40.5 Gy in 3 weeks
+/- lymph node irradiation (5x2.7 Gy/week → 40.5 Gy in 3 weeks)

The standard of care arm presented here is a brief summary, which does not claim to be exhaustive. For a detailed summary of the radiotherapeutic treatment in this study, refer to Chapter 6

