6.4.2 Whole Breast Radiotherapy (WBRT)

In the experimental arm, WBRT should preferably begin 2-4 weeks after the last application of NACT. In case of persistent toxicity that is regarded critical for radiotherapy, up to 6 weeks are allowed. Surgery should be performed after disappearance of the acute radiation induced erythema, preferably 3-6 weeks after completion of pre-operative radiotherapy. In the standard arm, post-operative WBRT should start 3-6 (up to 8) weeks after surgery.

6.4.3 Indication for breast/chest wall and regional lymph node irradiation:

Experimental arm (preoperative radiotherapy)

Preoperative radiotherapy Arm

- all patients receive whole breast radiotherapy (5x 2.7 Gy to 40.5 Gy +/- Boost RT)
- indication for regional lymph node radiotherapy depends on the initial findings before the start of the NACT +/ targeted therapy (5x 2.7 Gy to 40.5 Gy)

Lymph node region	indicated, if initially
Level I*- IV	cN+
Internal mammary chain LN**	cN+ and >=1 of the following factors

1) Central or medial tumor location

- 2) ER/PR negative tumor
- 3) cT3 tumor
- 4) cT4 tumor
- 5) cN2
- 6) inflammatory tumors
- 7) enlarged lymph nodes in the internal mammary chain

* Subtotal RT of Level I- II (see CTV definitions)

** No Internal mammary chain radiotherapy for left sided cancers treated with trastuzumab +/- pertuzumab and/or relevant cardiac comorbidity

Note: indications depend on the pretherapeutic findings irrespective of response to neoadjuvant systemic therapy

* Limited radiotherapy of Level I+II (see CTV definition)

** No IMC radiotherapy for left sided cancers treated in case of trastuzumab+/- pertuzumab or relevant cardiac comorbidity

Standard arm (postoperative radiotherapy):

The indication for whole breast / chest wall, for regional lymph nodes and boost radiotherapy should be administered according to the current recommendations of the AGO guideline.

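### The dose tables in section 6.4.7 carry a nodal high-dose volume (PTVn_high, 15 x 3.2 Gy in the IOERT table) that the protocol never defines, so the same node can be planned to 40.5 or 48 Gy

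*Protocol*

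**What the plan says.** **One nodal dose in the text.** The list in Protocol 6.4.7 gives "PTV (RNI): 40.5 Gy in 15 fractions (2.7 Gy daily"). Section 4.4 gives the standard arm "lymph node irradiation (5x2.7 Gy/week → 40.5 Gy in 3 weeks"). For the experimental arm, section 6.4.3 says "indication for regional lymph node radiotherapy depends on the initial findings before the start of the NACT +/ targeted therapy (5x 2.7 Gy to 40.5 Gy"), and section 6.4 gives the same dose.

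**A second nodal volume in the tables.** The sequential, SIB and IOERT tables in 6.4.7 all carry a combined low-dose volume, "PTVb+n_low 15 2.7Gy 40.5Gy", and all three also name PTVn_high. In the IOERT table that row reads "PTVn_high 15 3.2Gy", with no total. In the SIB table the primary-tumour volume reads "PTVp_high 15 3.2Gy 48Gy", and PTVn_high is listed beneath it without figures.

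**The volume definitions.** For the experimental arm, section 6.4.6 defines GTVn as the marked and enlarged nodes at the time of radiotherapy, and then "CTVn = GTVn + 5mm + Level 1-2 (upper border 1 cm below V. axillares) + Level 3-4 + IMC (if indicated according to protocol"). PTVn is CTVn with a further margin. The primary tumour has a separate high-dose CTV and PTV; the nodes do not. The only mention of a nodal boost in the running text is in the organs-at-risk sentence on immediate reconstruction in the standard arm: "in case of axillary lymph node irradiation with a regional boost, the brachial plexus". It gives no dose, volume or indication.

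**The concern.** A planner with a cN+ patient and a marked or enlarged node has two instructions. By 6.4.6 and the dose list, the node lies inside CTVn and PTVn and receives 40.5 Gy. By the table, a nodal high-dose volume exists at 3.2 Gy per fraction. Nothing says when the second applies or how to draw it.

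This bears on patient safety, because a prescribed radiation dose is left open. It also bears on the comparison. Regional recurrence, brachial plexopathy above grade I and arm lymphoedema above grade I are secondary endpoints (section 3.2). If sites read the tables differently, nodal dose would vary for reasons unrelated to the timing of radiotherapy. In 6.4.6 GTVn is defined only for the experimental arm, so the ambiguity may not fall equally on the two arms.

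**Working it through.** **Inputs**, all from the Protocol:
- Nodal dose: 15 x 2.7 Gy (6.4.7 list; also 4.4, 6.4, 6.4.3).
- PTVn_high: 15 x 3.2 Gy (6.4.7, IOERT table).
- Sequential boost: 3 x 3.5 Gy. IOERT: 1 x 10 Gy (6.4.7).
- Brachial plexus with nodal irradiation: at most 41 Gy (6.4.11, Table 2).

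**Formula:** total dose = number of fractions x dose per fraction, summed over the components of a table.

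**Reproducing the protocol's own totals:**
- Low-dose volume: 15 x 2.7 = 40.5 Gy, as printed.
- SIB, primary tumour: 15 x 3.2 = 48.0 Gy, as printed.
- Sequential: 40.5 + 3 x 3.5 = 51.0 Gy in 15 + 3 = 18 fractions, as printed.
- IOERT: 10 + 40.5 = 50.5 Gy in 1 + 15 = 16 fractions, as printed. This uses only the IOERT and PTVb+n_low rows; the PTVn_high row does not enter the total.

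**The row without a total:**
- PTVn_high: 15 x 3.2 = 48.0 Gy.
- Against the stated nodal dose: 48.0 - 40.5 = 7.5 Gy; 7.5 / 40.5 = 18.5%.
- Against the plexus figure: 48.0 - 41 = 7.0 Gy; 7.0 / 41 = 17.1%. The 40.5 Gy prescription lies 0.5 Gy below 41 Gy.

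**Checking the definitions.** GTVn plus 5 mm is part of CTVn, and CTVn lies inside PTVn. A marked or enlarged node is thus already inside the volume prescribed 40.5 Gy. PTVn_high appears only in the tables of 6.4.7, and no CTVn_high is defined anywhere. The boost indications that are given concern the breast or chest wall: residual tumour with planned breast conservation (3.1), the site's own rule for complete remission on imaging (6.4.6), guideline indications in the standard arm (4.4, 6.4.3), and R1 or R2 resection after mastectomy (6.4.6). None is a nodal finding.

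**Labels.** Section 6.4.6 names the high-dose planning volume for the primary tumour PTVb_high; the tables call it PTVp_high.

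**The case against.** The strongest reply is that the dose list gives base doses only. The breast entry also says 40.5 Gy, yet nobody reads the 48 Gy tumour volume in the SIB table as a contradiction. On that reading PTVb+n_low is the base and PTVn_high a boost to gross nodes, which would explain why GTVn is defined separately and why a regional boost is mentioned. This is plausible, but it does not close the gap. For the breast, the protocol supplies a high-dose volume, indications and totals. For the nodes it supplies a label and, in one table, a fraction dose.

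The reply does dispose of several stronger readings that a reader might infer:
- *The nodal high dose is tied to IOERT.* Not established. The empty cells in the sequential and SIB tables may be merged cells lost when the PDF was read, and they are not counted as errors here.
- *Section 6.4.11 rules out a nodal boost because it gives a total dose of 40.5 Gy.* It does not. The same protocol prescribes breast boosts to 48 and 51 Gy, so that line reads as the base reference dose.
- *A nodal dose of 48 Gy cannot meet the plexus limit.* The 41 Gy applies to the plexus, not to the node. Section 6.4.6 keeps the axillary volume below the axillary vein unless a positive node with its margin crosses that boundary. Table 2 is headed as recommended, and 6.4.11 puts target coverage first. A conflict arises only where the plexus lies in or near the boosted volume. For the same reason, converting the full nodal dose into an equivalent plexus dose would assume an exposure that the protocol does not state.
- *Quality review has no reference dose.* Section 6.4 refers sites to separate RTQA Guidelines, which are not shown and may supply one. They would not remove the inconsistency within the protocol.

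It also stands that the number of affected patients is unknown and that no effect on DFS has been shown.

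**Conclusion.** The point holds as an unresolved dose and an undefined volume. The same marked or enlarged node can be planned to 40.5 or 48 Gy, 7.5 Gy or 18.5% apart, and the protocol supports each reading. This rests on one assumption: that the IOERT row is to be read as printed, 15 fractions of 3.2 Gy, with the 48 Gy total calculated here. The excess over the plexus constraint, 7.0 Gy or 17.1%, is a worst case that applies only if the plexus receives the full nodal dose.

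It goes beyond missing detail, because a site following the text faithfully can arrive at either dose. The discrepancy may also surface late: under section 7, feedback on dose plans is retrospective and is specified for each site's first 10 patients. This review does not judge which dose is right.

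**What to change.** Reconcile sections 4.4, 6.4, 6.4.3, 6.4.6, 6.4.7 and 6.4.11 (Table 2) in one of two ways, the choice resting with the clinical team:
- remove PTVn_high from the tables in 6.4.7 and settle the passing mention of a regional boost in 6.4.6; or
- define PTVn_high fully in 6.4.6 (volume and indication, and the arms to which it applies), state its dose and total in 6.4.7, and say how it relates to the plexus constraint.

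In either case use one label for the primary high-dose volume in place of PTVb_high and PTVp_high, check the RTQA Guidelines against the reconciled text, and make that text the reference for the dose-plan review in section 7.

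The cost is a protocol amendment to the tables and definitions and a note to sites. No extra patients, visits or procedures are needed, and the sample size and analysis do not change.

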6.4.8 Documentation Requirements and Portal Films

Portal images of each field or orthogonal images that localise the isocenter placement must be obtained on the first day of therapy. Isodose plans, DVHs of the target volumes and critical normal structures are mandatory for planning. Weekly positioning verifications of the patients are required.

6.4.9 Diagnostics during WBRT

Weekly clinical examination of the breast (see 16.3 and Appendices).

6.4.10 Critical Normal Structures and Adverse Effects of Radiotherapy

Critical normal structures include the skin, lung, heart and brachial plexus. Acute side effects such as skin toxicity and breast oedema are common during treatment. These conditions are usually transient and resolve within a few weeks following the completion of radiotherapy. Pneumonitis requiring treatment as subacute side effect is rare. Heart toxicity and brachial plexus damage is expected to be rare.

6.4.11 Organs at risk

Single reference dose per fraction: 2.7 Gy (ICRU). Total dose is 40.5 Gy.

Dose constraints:

Please try to adhere to the following constraints. In case of conflict with the CTV/PTV dose prescription, priority has to be given to cover the CTV/PTV. The PTV to CTV margin may be compromised in select cases if deemed clinically acceptable. If the dose constrains to the lungs

and the heart are not kept, it is allowed to truncate the internal mammary chain CTV caudally to encompass just the region of the first 3 and not the first 4 intercostal spaces.

Please do not compromise the PTV in order to spare the LAD, caput humeri or thyroid.

Table 2: Recommended dose constraints for organs at risk

Organ at risk	Accepted dose	
	Breast/chest wall without lymph node irradiation	Breast/chest wall with lymph node irradiation including IMC
Heart	mean < 1 Gy (right side). mean < 3 Gy (left side)	mean <3 Gy (right side). mean <6 Gy (left side)
LAD	mean <1 Gy (right side) mean <8 Gy (left side)	mean < 6 Gy (right side) mean < 10 Gy (left side)
Lung ipsilateral	mean <10 Gy V20 <20 %	mean ≤ 14 Gy V20 ≤ 30%
Lung contralateral	mean <5 Gy V20 <10%	mean <6 Gy V20 <15 Gy
Lung Bilateral	mean < 9 Gy V20 < 10%	mean <10 Gy V20 <17%
Brachial plexus	max. 5 Gy	≤ 41 Gy
Contra-Lateral breast	mean < 2 Gy	mean < 4 Gy
Spinal cord	max. 2 Gy	max. 30 Gy
Esophagus	max. 2 Gy	max. 40.5 Gy mean 9 Gy
Caput humeri ipsilateral	Mean 3 Gy	Mean 10 Gy
Thyroid	Mean <1 Gy	Mean 15 Gy

The following organs at risks have to be delineated:

- ipsilateral lung
- contralateral lung
- heart
- LAD (if visible)
- contralateral breast
- spinal cord
- caput humeri

In case of indication for regional lymph node irradiation, additional delineation of the following structures is necessary:

- esophagus
- plexus brachialis
- thyroid

